## 8.2 Pembrolizumab

Adverse events (both non-serious and serious) associated with pembrolizumab exposure may represent an immunologic etiology. These adverse events may occur shortly after the first dose or several months after the last dose of treatment. Pembrolizumab must be withheld for drug-related toxicities and severe or life-threatening AEs as per below. It will be up to investigator to determine if each AE is attributed to metformin (and follow guidelines above) or pembrolizumab to follow guidelines below.

Pembrolizumab administration should be delayed for the following:

- Any Grade  $\geq 2$  non-skin, drug-related adverse event, with the following exceptions:
  - Grade 2 drug-related fatigue or laboratory abnormalities do not require a treatment delay
- Any Grade 3 skin, drug-related adverse event
- Any Grade 3 drug-related laboratory abnormality, with the following exceptions:
  - Grade 3 amylase or lipase abnormalities that are not associated with symptoms or clinical manifestations of pancreatitis do not require a dose delay.
  - If a subject has a baseline AST, ALT, or total bilirubin that is within normal limits, delay dosing for drug-related Grade  $\geq 2$  toxicity

- If a subject has baseline AST, ALT, or total bilirubin within the Grade 1 toxicity range, delay dosing for drug-related Grade  $\geq 3$  toxicity
- Any adverse event, laboratory abnormality, or intercurrent illness, which, in the judgment of the investigator, warrants delaying the dose of study medication

### 8.2.1 Management for Immuno-Oncology Agents

Immuno-Oncology (I-O) agents are associated with adverse events that can differ in severity and duration than adverse events caused by other therapeutic classes. Pembrolizumab is considered an immuno-oncology agent in this protocol. Early recognition and management of adverse events associated with immuno-oncology agents may mitigate severe toxicity. Management algorithms have been developed to assist investigators in assessing and managing the following groups of adverse events:

- Gastrointestinal
- Renal
- Pulmonary
- Hepatic
- Endocrinopathies
- Skin
- Neurological.

Investigators should use standard of care algorithms listed in the IB as well as institutional guidelines.

### 8.2.2 Dose Modifications for Pembrolizumab

Dose reductions or dose escalations are not permitted.

### 8.2.3 Criteria to Resume Pembrolizumab

Subjects may resume treatment with study drug when the drug-related AE(s) resolve to Grade  $\leq 1$  or baseline value, with the following exceptions:

- Subjects may resume treatment in the presence of Grade 2 fatigue.
- Subjects who have not experienced a Grade 3 drug-related skin AE may resume treatment in the presence of Grade 2 skin toxicity.
- Subjects with baseline Grade 1 AST/ALT or total bilirubin who require dose delays for reasons other than a 2-grade shift in AST/ALT or total bilirubin may resume treatment in the presence of Grade 2 AST/ALT OR total bilirubin.
- Subjects with combined Grade 2 AST/ALT AND total bilirubin values meeting discontinuation parameters should have treatment permanently discontinued
- Drug-related pulmonary toxicity, diarrhea, or colitis, must have resolved to baseline before treatment is resumed.
- Drug-related endocrinopathies adequately controlled with only physiologic hormone replacement may resume treatment.

If the criteria to resume treatment are met, the subject may restart treatment immediately.

Treatment may be delayed for up to a maximum of 8 weeks from the last dose; if treatment is delayed > 8 weeks, the subject must be permanently discontinued from study therapy.

#### 8.2.4 Dose Discontinuation of Pembrolizumab

Treatment should be permanently discontinued for the following:

- Any Grade 2 drug-related uveitis or eye pain or blurred vision that does not respond to topical therapy and does not improve to Grade 1 severity within the re-treatment period OR requires systemic treatment.
- Any Grade 3 non-skin, drug-related adverse event lasting > 7 days, with the following exceptions for drug-related laboratory abnormalities, uveitis, pneumonitis, bronchospasm, neurologic toxicity, hypersensitivity reactions, and infusion reactions:
  - Grade 3 drug-related uveitis, pneumonitis, bronchospasm, neurologic toxicity, hypersensitivity reaction, or infusion reaction of any duration requires discontinuation.
  - Grade 3 drug-related laboratory abnormalities do not require treatment discontinuation except:
    - Grade 3 drug-related thrombocytopenia > 7 days or associated with bleeding requires discontinuation
    - Any drug-related liver function test (LFT) abnormality that meets the following criteria require discontinuation:
      - AST or ALT > 8 x ULN
      - Total bilirubin > 5 x ULN
      - Concurrent AST or ALT > 3 x ULN and total bilirubin > 2 x ULN
- Any Grade 4 drug-related adverse event or laboratory abnormality, except for the following events which do not require discontinuation:
  - Isolated Grade 4 amylase or lipase abnormalities that are not associated with symptoms or clinical manifestations of pancreatitis and decrease to < Grade 4 within 1 week of onset.
  - Isolated Grade 4 electrolyte imbalances/abnormalities that are not associated with clinical sequelae and are corrected with supplementation/appropriate management within 72 hours of their onset.
- Any dosing delay lasting > 8 weeks with the following exceptions:
  - Dosing delays to allow for prolonged steroid tapers to manage drug-related adverse events are allowed. Prior to re-initiating treatment in a subject with a dosing delay lasting > 8 weeks, the PI must be consulted. Tumor assessments should continue as per protocol even if dosing is delayed.
  - Dosing delays > 8 weeks that occur for non-drug-related reasons may be allowed if approved by the PI. Prior to re-initiating treatment in a subject with a dosing delay lasting > 8 weeks, the PI must be consulted. Tumor assessments should continue as per protocol even if dosing is delayed.
- Any adverse event, laboratory abnormality, or intercurrent illness, which, in the judgment of the Investigator, presents a substantial clinical risk to the subject with continued

pembrolizumab dosing.

### 8.2.5 Management of Infusion Reactions:

Since pembrolizumab contains only human immunoglobulin protein sequences, it is unlikely to be immunogenic and induce infusion or hypersensitivity reactions. However, if such a reaction were to occur, it might manifest with fever, chills, rigors, headache, rash, pruritus, arthralgias, hypo or hypertension, bronchospasm, or other symptoms. All Grade 3 or 4 infusion reactions should be reported within 24 hours to University of Cincinnati PI (coordinating center), as well as to the local PI and reported as an SAE if criteria are met. Infusion reactions should be graded according to NCI CTCAE (version 5.0) guidelines.

Treatment recommendations are provided below and may be modified based on local treatment standards and guidelines as appropriate:

**For Grade 1 symptoms:** (Mild reaction; infusion interruption not indicated; intervention not indicated)

Remain at bedside and monitor subject until recovery from symptoms. The following prophylactic premedications are recommended for future infusions: diphenhydramine 25-50 mg (or equivalent) and/or acetaminophen 325 to 1000 mg at least 30 minutes before additional pembrolizumab administrations. A H1 blocker may also be administered.

**For Grade 2 symptoms:** (Moderate reaction requires therapy or infusion interruption but responds promptly to symptomatic treatment [e.g., antihistamines, non-steroidal anti-inflammatory drugs, narcotics, corticosteroids, bronchodilators, IV fluids]; prophylactic medications indicated for  $\leq$  24 hours).

Stop the pembrolizumab infusion, begin an IV infusion of normal saline, and treat the subject with diphenhydramine 25-50 mg IV (or equivalent) and/or acetaminophen 325 to 1000 mg; remain at bedside and monitor subject until resolution of symptoms. Corticosteroid or bronchodilator therapy may also be administered as appropriate. If the infusion is interrupted, then restart the infusion at 50% of the original infusion rate when symptoms resolve; if no further complications ensue after 30 minutes, the rate may be increased to 100% of the original infusion rate. Monitor subject closely. If symptoms recur then no further pembrolizumab will be administered at that visit. Administer diphenhydramine 25-50 mg IV, and remain at bedside and monitor the subject until resolution of symptoms. The amount of study drug infused must be recorded on the electronic case report form (eCRF). The following prophylactic premedications are recommended for future infusions: diphenhydramine 25-50 mg (or equivalent) and/or acetaminophen 325 to 1000 mg should be administered at least 30 minutes before additional pembrolizumab administrations. If necessary, corticosteroids (recommended dose: up to 25 mg of IV hydrocortisone or equivalent) may be used.

**For Grade 3 or Grade 4 symptoms:** (Severe reaction, Grade 3: prolonged [i.e., not rapidly responsive to symptomatic medication and/or brief interruption of infusion]; recurrence of symptoms following initial improvement; hospitalization indicated for other clinical sequelae)

[e.g., renal impairment, pulmonary infiltrates]). Grade 4: (life threatening; presser or ventilator support indicated).

Immediately discontinue infusion of pembrolizumab. Begin an IV infusion of normal saline, and treat the subject as follows. Recommend bronchodilators, epinephrine 0.2 to 1 mg of a 1:1,000 solution for subcutaneous administration or 0.1 to 0.25 mg of a 1:10,000 solution injected slowly for IV administration, and/or diphenhydramine 50 mg IV with methylprednisolone 100 mg IV (or equivalent), as needed. Subject should be monitored until the investigator is comfortable that the symptoms will not recur. pembrolizumab will be permanently discontinued. Investigators should follow their institutional guidelines for the treatment of anaphylaxis. Remain at bedside and monitor subject until recovery from symptoms. In the case of late-occurring hypersensitivity symptoms (e.g., appearance of a localized or generalized pruritus within 1 week after treatment), symptomatic treatment may be given (e.g., oral antihistamine, or corticosteroids).

## PHARMACEUTICAL INFORMATION

A listing of reported adverse events and potential risks are described in the Investigators Brochure for Pembrolizumab and the package insert for Metformin respectively. The UC Project Manager will ensure current versions of each are available to sites.

### 9.1 Investigational Agent

#### 9.1.1 Metformin

Availability: Commercial Metformin ER will be used as supply and will be obtained from the site investigational drug pharmacy.

Agent Ordering and Agent Accountability: Metformin will be requested from the investigational drug pharmacy at each participating institution.

Agent Inventory Records: The investigator, or a responsible party designated by the investigator, must maintain a careful record of the receipt, dispensing and final disposition of all agents received from IDS.

Investigator Brochure Availability: Metformin ER is a commercial product. Therefore, no IB will be provided.

### 9.2 Commercial Agent

#### 9.2.1 Pembrolizumab

Availability: Commercial Pembrolizumab will be used.

Agent Ordering and Agent Accountability: Pembrolizumab will be used as standard of care at each participating institution.

## STATISTICAL CONSIDERATIONS

### 10.1 Study Design/Endpoints

Primary Endpoint: Overall Response by RECIST 1.1 and iRECIST

Responses will be summarized as frequencies and percentages.

Secondary Endpoints:

- Measurement of Adverse Events by CTCAE v5.0
- Progression Free Survival (PFS) at 1 year
- Overall Survival (OS) at 1 year

After cleaning and preprocessing of the collected data, descriptive statistics will be used to summarize all adverse events. Toxicities will be aggregated as the number and percentage of patients with each type of toxicity. Kaplan Meier methods will be used to estimate overall survival and progression free survival generating median survival estimates with 95% confidence intervals (95% CIs). Multivariable survival modeling (overall survival and progression free survival) will be performed using Cox proportional hazards models and to generate Hazard Ratios (HR) and 95% CIs, with adjustment for potential patient confounders such as age, sex, smoking status, etc.

Exploratory Endpoint:

- Characterization of peripheral blood immune cell phenotypes before and after metformin, pembrolizumab and combination treatment with a particular focus on Natural Killer (NK) cells and innate immunity.
- Characterization of tumor infiltrating NK cells before and after metformin, pembrolizumab and combination treatment.
- Cytokine levels before and after metformin, pembrolizumab and combination in the plasma.
- NK effector functions before and after metformin, pembrolizumab and combination.
- Stat-3 RNA levels and phosphorylation status in NK cells and tumor tissue before and after metformin, pembrolizumab and combination treatment.
- Level of NKG2D soluble ligands before and after metformin, pembrolizumab and combination in the plasma.

Scatter plots and histograms will be used to examine the exploratory endpoints for the presence of unusual outliers, normality and potential non-linearity. Continuous endpoints will be log-transformed if not normally distributed. The endpoints using samples before and after treatment will be compared using paired T tests. When endpoints are compared between three or more groups, ANOVA model will be used. The ANOVA will be followed up with post-hoc pairwise comparisons. A chi-square test will be used to investigate the categorical exploratory endpoints. For IHC, the percentage of positive cells per area will be multiplied by the staining intensity for each tumor to determine quantitative expression pre- and post-treatment.

To detect a difference of 15% in %NK Cell Killed Target Cells between control and treated groups,

we will need 19 pairs of patients. In an unpaired comparison, 10 patients per group will give us enough power to detect a difference of at least 30% between the groups. We note that the average %NK Cell Killed Target Cells in controls was assumed to be around 10% (Data not shown) and the standard deviation was estimated from the range of 5 to 15%. We also note that the calculations are based on the significance threshold of 0.05 and an 80% detection power using one-sided tests.

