## OBJECTIVES

### 2.1 Primary Objective

- (1) To determine anti-tumor activity by measuring overall response rate by RECIST 1.1 and iRECIST in recurrent and/or metastatic HNSCC patients receiving the combination of metformin and pembrolizumab.

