## 10.2 Sample Size/Accrual Rate

We expect that metformin and pembrolizumab combination therapy will improve ORR to 32%. Our preliminary sample size calculations indicate that 25 patients should be enough to approximately estimate the proportion of around 32% with a margin of error close to 20%. We note that ORR of pembrolizumab alone based on previous clinical studies varies between 15-20% in HNSCC; and retrospective studies show metformin increased response rates by about 10-15% in other tumor types. We also note that the calculations are based on the significance threshold of 0.05 and an 80% detection power using one-sided tests. We plan to enroll twenty-five patients total with goal of 19 evaluable (20% expected drop-out rate given dysphagia seen in head and neck cancer patients). If 6/19 achieve response, we will consider study successful and worth pursuing further in a phase II/III study. The above calculations are based on the significance threshold of 0.05 and using the critical values of the normal distribution. We expect to enroll the patients over 18-24 months.

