### 13.1 Antitumor Effect – Solid Tumors

For the purposes of this study, patients should be re-evaluated for response every 9 weeks. In addition to a baseline scan, confirmatory scans should also be obtained 4 weeks following initial documentation of objective response.

Response and progression will be evaluated in this study using the international criteria proposed by the revised Response Evaluation Criteria in Solid Tumors (RECIST) guideline (version 1.1) [Eur J Ca 45:228-247, 2009]. However, iRECIST will also be used if pseudoprogression is suspected. Changes in the largest diameter (unidimensional measurement) of the tumor lesions and the shortest diameter in the case of malignant lymph nodes are used in the RECIST criteria.

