#### 13.1.4 Response Criteria RECIST 1.1

##### 13.1.4.1 Evaluation of Target Lesions

Complete Response (CR): Disappearance of all target lesions. Any pathological lymph nodes (whether target or non-target) must have reduction in short axis to <10 mm (<1 cm).

Partial Response (PR): At least a 30% decrease in the sum of the diameters of target lesions, taking as reference the baseline sum diameters.

Progressive Disease (PD): At least a 20% increase in the sum of the diameters of target lesions, taking as reference the smallest sum on study (this includes the baseline sum if that is the smallest on study). In addition to the relative increase of 20%, the sum must also demonstrate an absolute increase of at least 5 mm (0.5 cm). (Note: the appearance of one or more new lesions is also considered progressions).

Note: Modified iRECIST is also being used in that given that immunotherapy is being administered in this protocol, patients may remain on study at first progression if investigator feels the patient is deriving clinical benefit. However, if in subsequent scans, the lesions continue to progress beyond previous scan, the patient will be considered to have progressive disease and should be taken off protocol. Any question should be discussed with the sponsor.

Stable Disease (SD): Neither sufficient shrinkage to qualify for PR nor sufficient increase to qualify for PD, taking as reference the smallest sum diameters while on

study.

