#### 13.1.4.3 Evaluation of Best Overall Response

The best overall response is the best response recorded from the start of the treatment until disease progression/recurrence (taking as reference for progressive disease the smallest measurements recorded since the treatment started). The patient's best response assignment will depend on the achievement of both measurement and confirmation criteria.

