#### For Patients with Measurable Disease (*i.e.*, Target Disease)

Target Lesions	Non-Target Lesions	New Lesions	Overall Response	Best Overall Response when Confirmation is Required*
CR	CR	No	CR	≥4 wks. Confirmation**
CR	Non-CR/Non-PD	No	PR	≥4 wks. Confirmation**
CR	Not evaluated	No	PR	
PR	Non-CR/Non-PD/not evaluated	No	PR	
SD	Non-CR/Non-PD/not evaluated	No	SD	Documented at least once ≥4 wks. from baseline**

PD	Any	Yes or No	PD	no prior SD, PR or CR
Any	PD***	Yes or No	PD	
Any	Any	Yes	PD	

\* See RECIST 1.1 manuscript for further details on what is evidence of a new lesion.

\*\* Only for non-randomized trials with response as primary endpoint.

\*\*\* In exceptional circumstances, unequivocal progression in non-target lesions may be accepted as disease progression.

Note: Patients with a global deterioration of health status requiring discontinuation of treatment without objective evidence of disease progression at that time should be reported as “*symptomatic deterioration.*” Every effort should be made to document the objective progression even after discontinuation of treatment.

iRECIST Note: Given that immunotherapy is being given in this protocol, patients may remain on study at first progression if investigator feels the patient is deriving clinical benefit. However, if in subsequent scans, the lesions continue to progress beyond previous scan, the patient will be considered to have progressive disease and should be taken off protocol. Any question should be discussed with the sponsor.

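### The 6/19 go rule does not say which of the two response criteria it counts; if either one counts, selective use of iRECIST can add responders but never remove them

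*Combined protocol and SAP*

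**What the plan says.** Section 2.1 gives the primary objective as "measuring overall response rate by RECIST 1.1 and iRECIST", and Section 10.1 repeats it: "Primary Endpoint: Overall Response by RECIST 1.1 and iRECIST". Neither says whether a patient must respond by both criteria, by either, or whether two rates are to be reported.

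Section 10.2 has one decision rule: "If 6/19 achieve response, we will consider study successful and worth pursuing further in a phase II/III study". It names no criterion.

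Section 13.1 makes RECIST 1.1 the standard and then adds: "However, iRECIST will also be used if pseudoprogression is suspected". Section 13.1.4.1 describes a modified iRECIST under which "patients may remain on study at first progression if investigator feels the patient is deriving clinical benefit"; for such a patient, "if in subsequent scans, the lesions continue to progress beyond previous scan, the patient will be considered to have progressive disease". The note under the response table in Section 13.1.4.3 repeats this. Both notes concern staying on study and declaring progression. Neither defines an iRECIST complete or partial response.

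Section 13.1.4.3 states: "The best overall response is the best response recorded from the start of the treatment until disease progression/recurrence". It does not say whether first progression or the later, further progression closes the window. Section 13.1.6 dates PFS at progression with the same gap.

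On confirmation, Sections 7.6.3, 13 and 13.1 call for a scan 4 weeks after a response, while a footnote to the table in Section 13.1.4.3 marks confirmation as "Only for non-randomized trials with response as primary endpoint".

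**The concern.** A go/no-go threshold has known error rates only if each patient's response status follows from a rule fixed beforehand. Here the same patient can be a non-responder or a responder depending on which criterion is used and on when the best-response window closes.

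The patient at issue progresses by RECIST 1.1, is kept on study because pseudoprogression is suspected, and later shrinks. Under RECIST 1.1 with the window closed at first progression, this is a non-responder. Under an iRECIST reading, it may be a responder. iRECIST enters only through suspicion and the investigator's view of benefit, in a study with no blinding and no independent response review described for the primary endpoint. It is therefore applied to some progressors and not to patients in general. Used this way it can move a patient from non-response to response. It has no route for moving one the other way.

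At stake is the decision to take the combination forward. With 19 evaluable patients, one reclassified patient can settle it.

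**Working it through.** **Inputs from the documents (Section 10.2).** 19 evaluable patients; go at 6 or more responses; pembrolizumab-alone response rate 15–20%; target 32%; one-sided 0.05; 80% power; margin of error close to 20% with 25 patients. Section 3.1 gives 18–22% as the current response rate, so 18% is shown as well.

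**Assumed input.** The percentage points *d* of patients who respond by iRECIST only. The documents give no figure; the range used is 0 to 5 points.

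**Step 1: the plan's own figures.** The half-width of a two-sided 95% interval at 32% is 1.96 × √(0.32 × 0.68 / n). It is 18.3% for n = 25 and 21.0% for n = 19, which loosely reproduces the stated margin. The stated error rates are not reproduced. With X ~ Binomial(19, p), P(X ≥ 6) is 0.054 at p = 0.15, 0.163 at p = 0.20 and 0.601 at p = 0.32. The false-go rate is thus 5.4% to 16.3%, and power is 60.1%, before iRECIST plays any part. That is a separate weakness of the rule; these values serve here as the RECIST 1.1-only baseline.

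**Step 2: either criterion counts.** The probability that a patient is counted becomes p + d, and the false-go rate is P(X ≥ 6) for X ~ Binomial(19, p + d).

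| True RECIST 1.1 rate p | d = 0 | d = 1 | d = 2 | d = 3 | d = 5 |
|---|---|---|---|---|---|
| 15% | 5.4% | 7.0% | 8.9% | 11.1% | 16.3% |
| 18% | 11.1% | 13.6% | 16.3% | 19.3% | 25.9% |
| 20% | 16.3% | 19.3% | 22.5% | 25.9% | 33.2% |

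**Step 3: how often one patient decides.** The chance of exactly 5 RECIST 1.1 responders in 19 is P(X ≥ 5) − P(X ≥ 6). At 15% it is 0.144 − 0.054 = 0.091 (from unrounded values), and at 20% it is 0.327 − 0.163 = 0.164. So at these rates between 9% and 16% of trials would end where a single added responder turns a no-go into a go.

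**Step 4: readings under which nothing rises.** If RECIST 1.1 alone governs the rule, or if Section 13.1.4.3 closes best response at first RECIST 1.1 progression, d = 0 and the first column applies. If both criteria are required, the count cannot exceed the RECIST 1.1 count. The text is compatible with each of these and selects none.

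**The case against.** The strongest reply is that this is ambiguity, not demonstrated inflation. Section 13.1 makes RECIST 1.1 the standard. The plain reading of Section 13.1.4.3 ends best response at progression, so a later shrinkage would not count. The modified iRECIST notes only govern staying on study. Section 10.1 says that responses will be summarised as frequencies and percentages, which fits reporting both criteria side by side. All of this stands, and it is why the size is given as conditional. It does not remove the point: the endpoint still names iRECIST, the go rule still names nothing, and the reading could be settled after the responses are known.

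Three stronger inferences are tempting and are not supported:

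- **That the false-go rate does rise.** This needs an either-criterion count, or a later choice of the more favourable one, and also some iRECIST-only responses. The documents state none of these, and nothing in them suggests that the sponsor intends such a choice.
- **That five RECIST 1.1 responses are in effect enough.** This assumes an iRECIST-only responder in every trial. Even then, that patient is a RECIST 1.1 non-responder, so the five must come from the other 18: P(X ≥ 5) with n = 18 is 12.1% at 15% and 28.4% at 20%. Using n = 19 gives 14.4% and 32.7%, which overstates that scenario.
- **That the footnote cancels confirmation because patients are randomised.** Sections 7.6.3, 13 and 13.1 call for confirmation scans, Section 13.1.4.3 makes best response depend on confirmation, and Section 10.4 says that randomisation does not affect the primary endpoint. The footnote needs a clarifying word, no more.

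A practical objection also stands. Applying iRECIST to every patient may need scans that are not scheduled: Section 7.9 lists progression among the reasons to stop treatment, and Section 7.6.5 moves patients with confirmed progression to survival follow-up that can be by telephone.

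**Conclusion.** The point holds in conditional form. The primary endpoint names two criteria, the single go rule names neither, and iRECIST enters only on suspicion. If a response by either criterion counts, the bias has one direction. For an assumed 0 to 5 points of iRECIST-only response, the false-go rate ranges from 5.4% to 16.3% at a true rate of 15%, and from 16.3% to 33.2% at 20%. Under the other three readings it does not change.

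These figures rest on exactly 19 evaluable patients, on the assumed range for *d*, and on taking the 15–20% benchmark as a RECIST 1.1 rate, which Section 10.2 does not state. The PFS dating gap is real but secondary: PFS carries no decision rule. The change should be made, since it concerns the trial's only success criterion and can be made in wording.

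**What to change.** - In Sections 10.1 and 10.2, state that the 6/19 rule counts RECIST 1.1 responses confirmed at least 4 weeks later, up to first RECIST 1.1 progression. Fixing either criterion in advance would close the gap. RECIST 1.1 is the simpler choice because Section 13.1.4 already defines its response categories and its use depends on no suspicion.
- Report iRECIST response separately as a supportive secondary result, from the scans the protocol already collects.
- In Section 13.1.6, date PFS at first RECIST 1.1 progression, with the confirmed-progression date as a sensitivity analysis.
- Clarify that the confirmation footnote in Section 13.1.4.3 applies to this trial, because response is pooled over the two arms.

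The cost is wording: no extra patients, no extra scans, and no change to the provisions on staying on study. The downside is that a patient who responds only after pseudoprogression counts in the secondary response rate but not in the primary one.
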